## DOCUMENT HISTORY

Document	Date of Issue	Summary of Changes
Revised Protocol, Version 3.0	13May2016	
Based on the current landscape of HCV treatment options and feedback from investigators and the research team, the following changes/modifications will be incorporated into the PROP UP protocol:
 
 
• Based on changes/anticipated changes in treatment practices, the scope of this study has changed in order to capture the most accurate information on recent treatment practices. The brief summary has been updated to reflect the overall changes in the study protocol.
 
• Updated Section 1.0, Introduction, to reflect recent changes in HCV treatments. Several new DAA medications have been FDA approved but not extensively evaluated for long-term outcomes using patient reported outcomes.
 
• Updated Section 2.0, Study Rational, to describe that PROP UP will evaluate, characterize and compare the short-term and long-term harms and benefits associated with several HCV treatment regimens.
 
• Updated Section 3.1, Specific Aims, to reflect the fundamental protocol changes. The study will be focused on characterizing several HCV treatment regimens in terms of many harms and benefits captured via patient-reported outcomes collected before, during and after HCV treatment. 
 
○ Updated Aim 1 to explain the study will evaluate changes from baseline to time points during treatment in order to characterize harms associated with each of the treatments. The study uses several different measures, and adds patient-reported pre-existing medical conditions to list of the measures.
 
○ Updated Aim 2. This aim will evaluate the difference in medication adherence between patients with and without a history of mental health/substance abuse by evaluating different measures as explained in the protocol.
 
○ Updated Aim 3 to characterize short-term benefits of cure in the combine sample of patients.
 
○ Updated Aim 4 to include pre-existing medical conditions and HCV-functional status, and the differences in all measures between patients with and without cirrhosis on various treatment regimens.
 
 
 
• Added Section 3.2, Auxiliary Aims to describe that the study will examine a number of benefits and harms associated with DAA treatment and viral cure as described in the previous aims as well as use the data to examine similarities and differences between treatment regimens using causal inference methods.
 


- Updated Section 4.2, Clinical Collaborating Settings, to include ninth site, UC-Davis in Table 1: Location of Liver Centers Participating in PROP UP.
- Updated Section 4.31. Inclusion Criteria, with expanded inclusion criteria. Any HCV genotype is now eligible. Patients on the follow regimens are also eligible: sofosbuvir/ledipasvir (Harvoni®) with or without ribavirin, ombitasvir/paritaprevir/ritonavir with dasabuvir (Viekera Pak®), VPK) with or without ribavirin, elbasvir/grazoprevir (Zepatier®) with or without ribavirin, daclatasvir/sofosbuvir, with or without ribavirin (DAC/SOF), sofosbuvir/velpatasvir (SOF/VEL).
- Updated section 4.3.2, Exclusion Criteria, to emphasize that patients participating in a pharmaceutical-sponsored trial of hepatitis C treatment will not be eligible.
- Updated section 8.1, Procedures for Baseline PRO Data Collection, to add a sentence that participants will be reminded their answers are confidential before each survey. Also added that participants may complete surveys over the phone with research coordinator as needed at baseline.
- Updated Table 2 in Section 8.2, Procedures for Baseline Collection of Clinical and Lab Data for the following: (a) add the new treatment regimens and prescribed treatment duration of 16 weeks, (b) update HIV status to collect HIV test conducted and HIV results status, (c) add stigma scale.
- Updated Section 12.0, Participant Reimbursement, to reflect that UNC or subsites will reimburse subjects, aided by the REDCap system and records of reimbursement should be retained by the party responsible for paying the participant.
- Updated Table 5 in Section 13.0, Clinical and Lab Data Collection at 12 Weeks Post-Treatment top add 16 weeks or other to Actual Treatment Duration in the table.
- Updated Section 15.0, sub-sections 15.2 through 15.10 have been overhauled to reflect overall changes in the statistical analysis plan for this study. Updates include: description of the analysis of PRO changes from baseline as a function of subgroup and/or treatment regimen, description of the supportive longitudinal analysis and interpretation of changes from baseline, strategies for analysis of subgroup heterogeneity of treatment effects, and an overview of the four planned milestone manuscripts from this dataset.
- Updated Section 15.12, Overview of Sample Size Considerations, to adjust the sample size considerations.
- Added Appendix for Sample Size Analyses on page 34 of the protocol to provide tables and graphs to supplement the statistical analysis plan for the study.
- Updated protocol with grammatical and minor content clarification changes through the entire document.

Revised Protocol, version 2.0	23Sep2015	
Based on Investigator feedback from a recent Site PI conference call on 22Sep2015, the following changes/modifications will be incorporated into the protocol:
 
 
Based on current treatment guidelines, the protocol is being updated to include the enrollment of patients who are prescribed any “Harvoni-containing regimen” (e.g., Harvoni + Ribavirin). Section 4.3.1: Inclusion Criteria, Section 4.3.3: Discontinuation of Subjects from Study, Section 2: Study Rationale, Section 3: Study Aims, Section 6: Recruitment, and Section 8.2: Table 2 - Clinical and Laboratory Data Collection at Time of Consent have all been updated to reflect this change.
 
Clinical judgment suggests that some patients may tend to under-report infectious disease status, specifically HIV. The study will continue to collect patient-reported HIV status, but will also confirm HIV status via the patient’s medical record and extraction the HIV antibody (Anti HIV) for verification. Section 8.2: Table 2 - Clinical and Laboratory Data Collection at Time of Consent has been update to reflect this change.
 
Based on clinical experience at each site, it may take up to 90 days to receive prior authorization of medications and for patients to initiate treatment. The baseline PRO assessment window will therefore be increased from 45 to 90 days prior to start of treatment to allow adequate time for treatment approvals and initiation of therapy. Section 8.1: Procedures for Baseline PRO Data Collection, Section 9: Enrollment Criteria and Section 10: PRO Data Collection Time Points have been updated to reflect this change.
 
The language has been clarified that patients must be 21 years of age or older (no upper limit) to be included in the study. The Brief Summary, Section 4.3: Study Population and Section 4.3.1: Inclusion Criteria have been updated to reflect this change.
 
Based on site feedback and in order to reduce missing data points from baseline assessment, the timeframe for valid HCV Viral Load has been expanded from 3 months to 12 months prior to consent. The timeframe for valid Aspartate Aminotransferase, Alanine Aminotransferase, Albumin, Total Bilirubin, Creatinine, International Normalized Ratio, Platelets and Hemoglobin lab tests has been expanded from 3 months to 6 months prior to consent. HCV genotype is not time-sensitive; most recent test should be extracted. Section 8.2: Table 2 - Clinical and Laboratory Data Collection at Time of Consent has been update to reflect this change.
 

Original Protocol, version 1.0	30Aug2015	Not applicable

## BRIEF SUMMARY

### Title of Study: The Patient-Reported Outcomes Project of HCV-TARGET ("PROP UP")

Newer, more effective all-oral regimens for hepatitis C viral (HCV) infection have been approved in recent years and more are expected in the future. Minimal patient-centered outcome research (PCOR) data are currently available for the majority of these new drug regimens and enormous evidence gaps remain. In-depth information about these regimens is critical to informed decision-making, patient-provider communication, and patient adherence. Regimens may be relatively similar on SVR rates, but may differ on other short-term and long-term harms and benefits that matter to patients making treatment decisions. Data collected from pharmaceutical-sponsored trials do not provide all the answers, nor do their data represent what will happen when a broad spectrum of patients are treated in real-world practice. Trials also exclude vulnerable subgroups, focus mainly on short-term efficacy and clinician-rated adverse events, rarely obtain the patient's perspective, and do not investigate long-term harms of treatment or benefits of viral cure. Therefore, obtaining the requisite information in order to make informed decisions may prove challenging to patients and providers. Given these limitations, patient-centered outcomes research (PCOR) studies that evaluate short-term and long-term treatment harms and benefits that matter most to patients, are needed.

PROP UP is funded by The Patient Centered Outcomes Research Institute (PCORI). PROP UP is a multi-centered patient-centered outcomes study designed to evaluate, characterize, and compare several patient-reported outcomes (PROs) during and after treatment for HCV with newly approved all-oral regimens. PROP UP uses a prospective, observational cohort study design to collect PRO data before, during and after HCV treatment to rigorously evaluate HCV-associated symptoms, treatment side effects, medication adherence, out of pocket costs, and long-term benefits of cure and harms of treatment in various HCV treatment regimens and among important patient subgroups. PROP UP was designed with significant involvement from patients with the disease and is a collaborative effort between behavioral and biomedical researchers, a HCV Patient Engagement Group (HCV-PEG), and a patient advocacy organization (HCV Advocate).

Nine U.S. liver centers will collaborate to conduct PROP UP. Approximately 1920 patients diagnosed with chronic HCV will be consented and will complete baseline PRO assessments. Patients who are 21 years of age, infected with chronic HCV, and prescribed one of several direct-acting antiviral (DAA) treatment regimens for chronic HCV will be recruited. We anticipate that approximately 15%-20% of the 1920 patients who are consented will not commence HCV therapy, primarily due to insurance denials. Therefore we intend to enroll 1600 patients into longitudinal data collection. Enrollment criteria will include informed consent, completion of baseline PRO surveys, and administration of one dose of a prescribed regimen. These 1600 participants will be followed up to 1 year after HCV treatment ends. Participants will complete several PRO surveys at the following 5 assessment periods: (T1) Baseline, (T2) week 4 on-treatment, (T3) last 2 weeks on-treatment, (T4) 3 months post-treatment, and (T5) 12 months post-treatment for a total study duration of up to 20 months. PRO survey data will be collected via 3 options, selected by each participant: personal technology (home computer, tablet, smartphone) into web-based data capture system; phone-administered surveys with the UNC Call Center; or as a last resort, computer at regular clinic visits. PROs surveys are designed to measure HCV-associated symptoms, pre-existing conditions, treatment side effects, functional status, medication adherence, and out of pocket costs.

Longitudinal data collection of multiple novel PROs before, during and after treatment for HCV are being collected to better understand a variety of issues that are important to patients, clinicians, and stakeholders. Specifically, we will evaluate: (a) prevalence of pre-existing baseline symptoms associated with HCV; (b) the development of new onset treatment side effects and exacerbation of pre-existing symptoms during HCV treatment; (c) medication adherence and out of pocket costs related to HCV treatment; (d) changes in HCV-associated symptoms and functional status in patients who are cured; and (e) long-term patient-reported harms associated with treatments and long-term benefits associated with viral cure.

Study results will be disseminated via partnership with patient advocacy organizations and the HCV-TARGET network, as well as through traditional scholarly output. The findings from this study will help patients, providers, and stakeholders involved in decision-making by providing them with novel information they need to decide whether or not to proceed with HCV treatment and if so, what the short-term and long-term benefits and harms of HCV treatment, may be.

## 1 INTRODUCTION

Chronic Hepatitis C virus (HCV) causes numerous liver-related complications and death, leading to tremendous burden on millions of people and the US healthcare system^1-3. HCV kills >12,000 people per year in the US from liver-related complications such as liver failure, cirrhosis, liver cancer. Over the course of 20-30 years, 20% of patients will develop life-threatening cirrhosis and 10% will develop liver cancer. Morbidity and mortality rates are expected to increase dramatically in the next few decades as Baby Boomers suffer the long-term consequences of HCV.

People infected with chronic HCV also frequently suffer from chronic, systemic symptoms, other chronic conditions, and poorer quality of life, compared to the general US population. In addition to liver-related morbidity and mortality, many people with HCV complain of diffuse physical (e.g., fatigue, abdominal pain, nausea, poor appetite, joint/muscle achiness) and neuropsychiatric symptoms (e.g., mental fatigue, depression, irritability, insomnia, cognitive impairment). Many patients with HCV also have higher rates of comorbid conditions (e.g., psychiatric, addiction, diabetes, skin, HIV, renal) compared to the general population. Not surprisingly, people with HCV report poorer health-related quality of life (HRQOL) on many domains of functioning compared to their healthy counterparts. This relationship remains significant even after controlling for substance abuse history. The reasons for poor HRQOL are complex and likely multi-factorial, but may include symptoms due to chronic systemic viral inflammation of the central nervous system, comorbid conditions, feelings of social stigma, and constant health-related anxiety and uncertainty that their health will deteriorate in the future.

Antiviral treatment for chronic HCV can permanently eliminate the virus. Patients who successfully complete treatment can achieve a sustained virological response (SVR) or “viral cure” 12 weeks after treatment ends. SVR is associated in some patients with reversal of liver damage, and reductions in liver disease, liver-related death, and death due to all causes (e.g., cardiovascular, diabetes). In addition, SVR is associated with improvements in HRQOL and the symptom of fatigue at 3 months post-treatment. Importantly, many other benefits that may accompany viral cure have not been evaluated.

In the last 3 years, several new DAA medications have been FDA-approved for the treatment of chronic HCV. Other medications for the treatment of HCV are expected to be approved in 2016. Cure rates have typically been between 70% - 90% in phase III drug trials, depending on patient characteristics such as genotype and cirrhosis status. Treatment lasts between 8 and 24 weeks as opposed to previous interferon-based regimens of 24 or 48 weeks. These newly-approved all-oral regimens appear much more tolerable and efficacious in phase III trials, compared to previous interferon-based regimens.

These exciting, newly-approved regimens have not been extensively evaluated, particularly with regard to issues that patients care about or longer-term harms and benefits. Differences between specific subgroups of patients have also not been evaluated. Although cure rates are relatively high and side effects fewer and less severe than prior interferon regimens, treatment side effects still exist and may be different between regimens, especially in vulnerable subgroups (e.g., those with cirrhosis, mental health or substance abuse issues). Moreover, the only treatment harms measured in previous trials were captured as clinician-reported adverse events (AEs), as opposed to patient reported. Fatigue, headache, nausea, insomnia, body weakness, diarrhea and rash were reported as AEs in >10% of participants in previous drug trials. Previous research demonstrates that clinician-reported AEs often underestimate the patients’ experience of side effects. Since most symptoms and side effects are a highly subjective, personal experience, the correlation between clinician-reported and patient-reported side effects is often quite low. Finally, patients care about long-term benefits of being cured and whether symptoms associated with HCV attenuate, but few studies address these patient-centered outcomes. Therefore, outcomes chosen by, and reported by patients with the disease, are needed.

Currently, major evidence gaps exist that significantly limit our understanding of the short-term and long-term harms and benefits of these new treatments and thus, patients and clinicians ability to make informed treatment decisions. Patient-centered outcomes research (PCOR) studies are needed to ensure that patients and clinicians understand all of the short term and long-term harms and benefits of these new regimens. The only data currently

available are from phase III clinical trials, which have inherent limitations: First, clinical trials notoriously under-represent or exclude many subgroups, such as patients with cirrhosis, psychiatric and addiction conditions, so-called 'high risk' patients. Phase III trials included between 0% and 20% of patients with cirrhosis; yet, these patients have the greatest need for treatment. Over 60% of HCV patients seeking treatment in clinical practice have psychiatric or addiction issues, yet these patients are often excluded from clinical trials. Thus, clinical trials data do not represent the broad spectrum of patients seeking treatment and do not reflect what happens in real-world clinical settings. Secondly, phase III clinical trials do not provide any comparison of different regimens or important patient subgroups, such as those with psychiatric or addiction histories. Third, clinical trials have focused narrowly on short-term efficacy (SVR) and AEs, but have not captured additional information that is important to patients. Fourth, the short-term harms of treatment in clinical trials have usually been captured via clinician-reported adverse events. Research in other medical populations demonstrates that clinical data under-represent the frequency and severity of side effects compared to patient-reported experiences. To date, no PCOR studies have been conducted to characterize, evaluate, and compare different treatment options or patient subgroups on PROs that are of great interest to patients and stakeholders. The sparse PRO data that has been published thus far were derived from drug trials, focused only on health-related quality of life (HRQOL) and one symptom (fatigue), and did not fully evaluate nor compare treatment regimens or patient subgroups. Finally, because clinical trials are focused on short-term efficacy and safety, they do not capture longer term benefits of cure or harms of treatment that are also extremely important for patients to consider when making decisions about treatment.

## 2 STUDY RATIONALE

PROP UP is a multi-site prospective observational PCOR study that will evaluate, characterize, and compare several short-term and long-term harms and benefits associated with several HCV treatment regimens. The PCOR study proposed by PROP UP is unique, powered by patients affected by HCV, and will provide novel information for patients, clinicians, and stakeholders to enhance informed decision-making about HCV treatment.

In this study, we will collect information directly from the patients via PRO surveys measuring symptoms associated with HCV, co-morbid medical conditions, side effects associated with treatment, functional status, and out of pocket costs and medication adherence during treatment. This information will allow us to better evaluate and characterize HCV symptoms that are present at baseline, symptoms that remit after viral cure, treatment side effects/toxicity associated with various treatment options, long-term harms that may be associated with treatment, and benefits associated with viral cure.

Study results will be disseminated rapidly via partnership with patient advocacy organizations and the HCV-TARGET network, as well as through traditional scholarly output. The findings from this study will be useful to patients, their families, providers, and stakeholders who are involved in decision-making about whether or not to proceed with HCV treatment, and if so, what the short-term and long-term benefits and harms of HCV treatment, may be.

## 3 STUDY AIMS

### 3.1 Specific Aims

This study is focused on characterizing several HCV treatment regimens in terms of HCV-associated symptoms, treatment side effects, medication adherence, out of pocket costs, and long-term benefits of cure and harms associated with all-oral treatments for chronic hepatitis C, as indicated by the following patient-reported outcomes (PROs) collected before, during and up to one year after HCV treatment:

Aim 1: Evaluate changes from baseline (T1) to during treatment (T2, T3) to characterize harms associated with each treatment regimen (*see manuscript #1 below*) in terms of the following measures:

- 1a. The Memorial Symptom Assessment Scale (MSAS)
- 1b. Specific side effects as measured by multiple PROMIS surveys

- 1c. HCV-specific functional status as measured by the HCV-PRO
- 1d. Pre-existing medical conditions
- 1e. Cumulative out of pocket costs during treatment

Aim 2: Evaluate differences in medication adherence between patients with and without history of mental health/substance abuse (MH/SA Hx) (see *manuscript #2 below*)

- 2a. Characterize and compare the two groups (with and without MH/SA Hx) on medication adherence while accounting for treatment regimen and pill burden.
- 2b. Estimate the effects of pill burden on medication adherence in the combined sample.
- 2c. Estimate the prevalence rates of reasons for nonadherence in the combined sample.
- 2d. Estimate the effect of medication adherence on the SVR rate at 3 months post-treatment.

Aim 3: Evaluate changes from baseline (T1) to 3 months after end of treatment (T4) to characterize short-term benefits of cure in the combined sample of patients (see *manuscript #3 below*)

- 3a: Amelioration of HCV-associated symptoms as measured by the MSAS and PROMIS surveys
- 3b. HCV-functional status as measured by the HCV-PRO

Aim 4: Evaluate changes from baseline (T1) to 1 Year (T5) after end of treatment to characterize long-term benefits or harms (see *manuscript #4 below*)

- 4a. Long-term symptoms as measured with the MSAS
- 4b. Long-term side effects as measured by PROMIS surveys
- 4c. Pre-existing medical conditions
- 4d. HCV-functional status, as measured by the HCV-PRO
- 4e. Differences in 4a-4d between patients with and without cirrhosis

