#### 14.6 Voils Medication Adherence Survey (VMAS) to measure medication adherence (Aim 1f)

Medication adherence (how well patients take their medications every day as prescribed) and the reason for missed doses, may vary between treatment regimens, treatment durations and among patient subgroups. The VMAS consists of 3 items that evaluated the *extent* of adherence using a 5-point Likert scale from 1=None of the time to 5=All of the time. The 3 items assess how often participants missed doses, skip doses, or do not take doses over the past 7 days and are averaged into a single score shown to be reliable ( $\alpha = 0.84$ ). A

dichotomous variable will be created to categorize patients as 100% or <100% adherent. The VMAS has undergone qualitative testing in patients with HCV on antiviral therapy and is currently being validated in a HCV population on all-oral antiviral therapy.

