#### **15.6 Overview of Plans for Manuscript #2: Medication Adherence during T1 to T2/T3**

Aim 2, Medication Adherence. The analyses concerning adherence will be based on the patient-reported Voils' Medication Adherence Survey (VMAS) at 3 months post-treatment.

Aim 2a. In the combined convenience sample of 1600 participants, two subgroups defined by mental health or substance abuse history (MH/SU Hx: yes, no) will be characterized and compared in terms of medication adherence using the VMAS. We anticipate 50% (n=800) of participants having a MH/SU Hx and 50% (n=800) without a MU/SU Hx. We hypothesize that the two subpopulations are equivalent with regard to medication adherence (<5% difference in medication adherence). Each participant's level of adherence will be classified as high (100% adherent) or low (<100% adherent) for purposes of the analysis. Overall, we anticipate that about 75% of participants will report perfect 100% adherence. Individual adherence may vary depending on treatment regimen, pill burden and patient characteristics. The adherence literature suggests that adherence decreases as the number of pills in the regimen increases (Claxton). The primary characterization of each subgroup, and their comparison, we rely on a logistic regression model for adherence conditional on *subgroup, pill burden, cirrhosis status, age, race, and sex at birth*. The analysis will focus on point estimates and confidence intervals. In particular, the rate (P) of high adherence for each subgroup, and the magnitude of difference between those two rates, are of greatest interest. Of less interest, an equivalence test procedure will be used to test the null hypothesis that the subpopulations do not have equivalent rates. 'Equivalent' will be defined to mean that the difference between population rates, ( $P_1 - P_2$ ), is less than 5%, and thus the null hypothesis is  $|P_1 - P_2| > 5\%$ . For purposes of generating new hypotheses, variations on the model will be explored using additional or alternative covariates such as *marital status, educational status, income level, living situation, employment status, health coverage*, and selected two-way interactions thereof.

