population rates that differ by less than 0.05 will be considered equivalent

Figure	MS	Groups	N	procedure	X_80	X_90
4-1	1, 2	1	1500	Confidence interval [1]	0.02 [0.03,0.02]	0.02 [0.03,0.02]
4-2	1, 2	1	960	Confidence interval [1]	0.03 [0.03,0.02]	0.03 [0.03,0.02]
4-3	1, 2	1	160	Confidence interval [1]	0.06 [0.08,0.05]	0.07 [0.08,0.05]
4-4	1, 2	1	120	Confidence interval [1]	0.07 [0.09,0.06]	0.08 [0.09,0.06]
4-5	1, 2	1	100	Confidence interval [1]	0.08 [0.10,0.07]	0.08 [0.10,0.07]
4-6	1, 2	1	80	Confidence interval [1]	0.09 [0.11,0.07]	0.09 [0.11,0.08]
4-7	1, 2, 3A	2	800 + 800	test Ho: 'rate difference is zero' [5]	0.06 [0.07,0.05]	0.07 [0.08,0.05]
4-8	1, 2, 3A	2	800 + 800	test Ho: 'rates are equivalent(0.05)' [5]	0.00 [0.00,0.00]	0.00 [0.00,0.00]

[1] Pr[ Confidence Interval's half-width will be < X\_80 ] = 0.80

[2] Pr[ p < alpha | population mean change = X\_80 ] = 0.80

[3] Pr[ p < alpha | population mean difference = X\_80 ] = 0.80

[4] Pr[ p < alpha | population rate change = X\_80 ] = 0.80

[5] Pr[ p < alpha | population rate difference = X\_80 ] = 0.80

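### Aim 2a promises a regimen-adjusted comparison of adherence, but the primary model in section 15.6 leaves treatment regimen out

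*Combined protocol and SAP*

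**What the plan says.** Section 3.1 states that Aim 2a compares the two history groups on adherence "while accounting for treatment regimen and pill burden". Regimen and pill burden are listed as two separate things.

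Section 15.6 gives the primary model for that aim as a "logistic regression model for adherence conditional on *subgroup, pill burden, cirrhosis status, age, race, and sex at birth". Regimen is not in the list. The same paragraph says "Individual adherence may vary depending on treatment regimen, pill burden and patient characteristics", and section 14.6 says that adherence and the reasons for missed doses "may vary between treatment regimens, treatment durations and among patient subgroups". Section 15.6 also allows exploratory variations, for generating hypotheses, with "additional or alternative covariates such as *marital status, educational status, income level, living situation, employment status, health coverage". That list is open-ended, but regimen is not on it.

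On how the result is judged, section 15.6 states: "We hypothesize that the two subpopulations are equivalent with regard to medication adherence (<5% difference in medication adherence". The adherence table in the Appendix adds that "population rates that differ by less than 0.05 will be considered equivalent". Section 15.6 puts most weight on the two rates and their difference, and less on the formal equivalence test.

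Section 15.12 expects the history subgroup to be roughly as common in one regimen cohort as in another, at about 50%. It describes its cohort sizes as approximate and liable to change.

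**The concern.** The aim and the model that is meant to answer it do not match. Regimen is not assigned at random here. If clinicians or insurers steer patients with a history towards different regimens, and adherence differs between regimens beyond what pill count explains, part of that regimen effect will appear as a difference between history groups. The difference is read against a 5-point margin, so a shift of one or two points matters to the interpretation. A reader of manuscript #2 would also take the result to be regimen-adjusted when it is not. If the mismatch stays open, the choice between the two models could be made after the data are seen, which section 15.1 sets out to prevent.

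**Working it through.** **Step 1: the texts side by side.**
- Aim 2a, section 3.1: adjust for regimen and pill burden.
- Primary Aim 2a model, section 15.6: subgroup, pill burden, cirrhosis status, age, race, sex at birth.
- Primary models for manuscripts #1, #3 and #4 (sections 15.5, 15.7, 15.8): all include treatment regimen.

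Only manuscript #2 leaves regimen out, although its first sub-aim names it.

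**Step 2: the plan's own adherence figures.** Inputs: 800 per group (15.6), margin 0.05, alpha 0.05 (15.12), adherence 0.80 with range 0.60 to 0.90 (Appendix) or about 0.75 (15.6).
- Half-width 1.96 × √(p(1−p)/n) at p = 0.80: 0.025 for n = 960, 0.062 for 160, 0.088 for 80. The plan's 0.03, 0.06 and 0.09 agree to rounding.
- Test of no difference, 0.80 against 0.74, 800 per group: power 81.4%. The plan's 80% point of 0.06 agrees.
- Equivalence by two one-sided tests at a true difference of 0, with SE = √(2p(1−p)/800). At p = 0.80, SE = 0.020 and power is 60.8%. At p = 0.75 it is 49.4%, and at p = 0.90 it is 90.9%. The power above 90% stated in section 15.12 is reached only at the top of the conjectured range. That is a separate matter: this point does not depend on it, and adding regimen does not mend it.

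**Step 3: size of the bias.** Suppose a regimen has share s₁ in one history group and s₀ in the other, and adherence on it differs by g from the remaining regimens at equal pill burden. Omitting regimen then shifts the rate difference by (s₁ − s₀) × g. The documents give neither factor, so both are assumptions, except that section 15.12 implies s₁ − s₀ ≈ 0.

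| Mix difference | g = 5 points | g = 10 points | g = 15 points |
|---|---|---|---|
| 0 (plan's expectation) | 0 | 0 | 0 |
| 5 points | 0.25 | 0.5 | 0.75 |
| 10 points | 0.5 | 1.0 | 1.5 |
| 20 points | 1.0 | 2.0 | 3.0 |

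Entries are percentage points. The non-zero ones are 5% to 60% of the 5-point margin.

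**Step 4: how large a mix difference is possible.** With 800 per history group, a cohort's share can differ by at most (cohort size)/800. Using the Table 6 sizes:
- Viekira Pak and daclatasvir/sofosbuvir: 80/800 = 10 points each.
- Sofosbuvir/velpatasvir: 120/800 = 15 points.
- Zepatier: 160/800 = 20 points.

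Each ceiling needs every patient on that regimen to fall in one history group. A 20-point difference is otherwise reachable mainly as Harvoni against all others pooled, for example 70% against 50% (560 + 400 = 960).

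**Step 5: effect on the equivalence test.** These figures use the unadjusted two-proportion approximation at p = 0.80 and 800 per group, so they are a guide only.
- True difference 5 points, bias towards zero: the chance of declaring equivalence rises from 5.0% with no bias to 6.4% (0.25 points), 12.4% (1 point), 25.1% (2 points) and 41.1% (3 points).
- True difference 0, bias away from zero: power falls from 60.8% to 60.4%, 55.1%, 41.1% and 25.1% for the same biases.
- At p = 0.75, a 1-point bias moves these two figures from 4.9% to 11.3% and from 49.4% to 45.0%.

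**The case against.** The strongest reply is that little bias should be expected. Section 15.12 anticipates history to be evenly spread over the regimens, and under that expectation the bias is about zero. Pill burden, the regimen feature that section 15.6 links to adherence through the literature, is already in the model. This stands as a limit on size. It does not settle the mismatch, because the balance is an expectation in an observational cohort whose mix the plan says may change.

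Other sections might seem to cover the gap. Section 15.2 lists regimen in a general model, but only as something that may be used, for change from baseline, with a similar approach for binary scales. Section 15.10 extends causal methods to subgroup comparisons without naming Aim 2a or regimen as a covariate. The variations in 15.6 are exploratory. None puts regimen in the primary model. Section 15.2 also cites manuscript #2 as an analysis that may disregard regimen, but the subject there is the benefit of viral cure, which sections 3.2 and 15.7 assign to manuscript #3.

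Regimen might lie on the path from history to adherence, so that adjusting changes the question. Aim 2a nevertheless states the adjusted question. Collinearity with pill burden weakens those two coefficients, but matters much less for the history contrast.

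Three stronger readings are tempting. First, a reader might take the bias to be at least 1 point and as much as 4 (20 × 20 points, or 80% of the margin). The documents support neither a floor above zero nor a 20-point adherence gap, and Step 4 shows how hard a 20-point mix difference is to reach. Second, a reader might treat the 5% test as the main decision, but section 15.6 makes it secondary to the estimates. Third, a reader might suppose that a regimen term also deals with duration and ribavirin. It does not: prescribed duration is a separate field (Table 2, section 9), and four of the five regimens can be given either way with respect to ribavirin.

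**Conclusion.** The mismatch is real: the primary model in section 15.6 does not produce the regimen-adjusted contrast that Aim 2a promises, and no other section supplies it. Regimen imbalance can bias the rate difference, and through it the secondary equivalence test. The documents do not show that it will. The size runs from about zero, under the plan's expected balance, to about 0.25 to 3 percentage points under the assumed mix differences of 5 to 20 points and adherence gaps of 5 to 15 points. The upper end needs the largest value of both. This should be corrected before analysis, mainly to make the aim and the model agree and to guard against the balance expectation failing.

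**What to change.** In section 15.6, add treatment regimen to the primary Aim 2a model as a five-level factor, and keep the pill-burden-only model as a sensitivity analysis. Check the small cohorts for sparse cells. Viekira Pak and daclatasvir/sofosbuvir are expected to have about 40 patients per history group, which at 75% adherence is about 10 imperfect adherers per cell (40 × 0.25).

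Prescribed duration and ribavirin use can enter a further sensitivity model. Splitting regimens by ribavirin would give up to nine categories (4 × 2 + 1), or 8 degrees of freedom.

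Leave regimen out of the Aim 2b model, where pill burden is the exposure and is itself a feature of the regimen.

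The cost is 4 degrees of freedom from about 1600 participants, and less precise pill-burden and regimen coefficients, which are nuisance terms for Aim 2a. No new data are needed, because regimen is already recorded at consent and at enrolment (section 8.2, section 9). If the sponsor prefers not to adjust, the fallback is to reword Aim 2a to match the model and report the regimen-adjusted analysis as a sensitivity analysis.
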